Participating sites will be chosen based on availability of EVH/OVH harvesters (see Appendix F), but also based on CABG volume as well as ability and willingness of the local site surgeon investigator to meet enrollment goals. The local site surgeon investigators and research coordinators will be trained on study specific recruitment at the Investigator Meeting. Subsequently, each local site surgeon investigator will present the study protocol to the appropriate local clinical care providers for subjects undergoing CABG surgery at their site so those involved in the care of the subjects are familiar with the protocol requirements. Each site will have one full time dedicated research coordinator to facilitate enrollment. Each site will obtain a waiver of informed consent/HIPAA for screening purposes from the local IRB and following this, will work with the clinical care team to identify subjects referred for CABG surgery who meet study criteria. Every CABG-only subject the site surgeon investigator deems as

meeting study criteria will be approached. After preliminary consultation and screening with a potential participant's clinical team, the participating site's research coordinator will approach each non-emergent subject scheduled for a CABG-only procedure to discuss enrollment in the REGROUP study. After providing the potential subject adequate time to read the documents and to ask any questions, the research coordinator will obtain informed consent and collect all the baseline assessments. Randomization to either the EVH or OVH technique, stratified by harvester within site, will occur at the time of surgery after a qualified harvester is assigned to the case.

We recognize the VA policy to include women and minorities in clinical research. Although we do not anticipate a large number of women or minorities to be recruited for this study due to the demographics of subjects receiving care at the VA, efforts will be made to recruit both women and minorities for the REGROUP trial. At present, there are no ongoing or submitted research studies that directly relate to the REGROUP trial.

VII. Saphenous Vein Harvesting Techniques

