MACE, the composite endpoint that includes Death (all cause), Myocardial Infarction (MI) and Revascularization for myocardial ischemia, will be the primary outcome measure after randomization and the index CABG. Each randomized subject (either in Endoscopic or in Open harvesting group) will be followed after the index CABG to capture the time-to-MACE event where an ‘EVENT’ will be defined as either death (all cause) or an MI or a revascularization procedure during the follow-up period. Total follow-up period will be 6.5 years of which the first 4.5 years will be active follow-up (using in-clinic visit or by telephone) period and will be carried out by the site personnel. The remaining 2 years will be passive follow-up which will be carried out centrally by the chair’s office staff using the VA patient database. A minimum of 1 year of active follow-up will be used for subjects who will be randomized at the tail end of the 3-year projected enrollment period of the study. The subjects

who will either be lost to follow-up or will not experience an 'EVENT' before the end of the follow-up period will be considered as right censored.

The primary analysis of such time-to-Mace event data will include the events only from the active follow-up period (which is 4.5 years). The secondary analysis will include events from the entire 6.5 years of follow-up period.

Survival analysis techniques will be used to analyze the time-to-MACE event data for both primary and secondary analyses.

Kaplan-Meier analysis, a nonparametric method, will be used to estimate the survival (not experiencing MACE) over time in the two harvesting groups and a log-rank statistic will be used to test the equality of the survival function estimates in the two groups (the null hypothesis).

Cox's Proportional Hazards models will be used to investigate the effect of harvesting technique on the time until MACE adjusted for other potential influential variables, such as, age, gender, harvester's experience etc.

3. Secondary Outcomes Measures

One and Three-year MACE: This composite endpoint consists of

- i. Death (all cause);
- ii. Myocardial Infarction and
- iii. Revascularization for myocardial ischemia.

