Subjects who suffer any one of these three outcomes within the first year or in the first three years after the index CABG will be counted towards calculating the proportions of subjects with MACE (yes/no) in each harvesting technique group – subjects with endoscopic vein grafting or subjects with open vein grafting. Only the first event will be considered as the MACE event. These two proportions will be compared using a chi-square test.

Post-operative Leg Wound Complications: All subjects in both harvesting technique groups – EVH or OVH – will be examined for complications of the leg wound from harvesting at discharge and at six weeks post-surgery. Post-operative leg wound complication status (yes/no) will be recorded at discharge and at six weeks post-surgery. Proportion of subjects with leg wound complications will be computed for each treatment group and these proportions at each time point will be compared using chi-square tests. The impact of confounding variables, such as, BMI, diabetes status, smoking status, on the post-operative leg wound infection will be analyzed using a logistic regression.

Severity of Incisional Leg Pain: Severe leg pain, due to incisions made during vein grafting, data will be collected at discharge and at six-week post CABG. Proportion of subjects with severe pain (pain score 3 and above = yes) at each time point will be compared using chi-square statistics.

Quality of Life: QoL scores using VR-12 and Seattle Angina Questionnaire will be computed at baseline, six week, and 12 months post-surgery for the subjects in the two harvesting technique groups (EVH and OVH). Subjects in both groups will be categorized as "improved", "no change" and "worse" based on their baseline scores. The proportion of subjects in these three categories will be compared between the two groups using chi-square statistics. The actual scores from these measures will also be used to compare subjects in the two harvesting technique groups using analyses of covariance techniques, where the baseline (pre-surgery) scores will be used as a covariate.

E. Interim Monitoring

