Randomization and Data management will be performed by the VA CSPCC [name]. An Interactive Touchtone Telephone Randomization System (ITTRS) will be used to set up the randomization system. Clinical DataFax System, a data management software will be used for data management. The CSPCC will have overall responsibility for the data at the end of the study.

Randomization

After a patient at any of the participating centers is consented, successfully screened and has provided baseline information, s/he will be assigned to a harvester. Once a harvester is assigned and available for the harvesting of the required vein, the patient will be randomized. The research coordinator will place a call to the ITTRS (a dedicated 1-800 phone number will be provided) to randomize the patient in one of the two harvesting techniques – endoscopic and open vein harvesting techniques. Once the required information is entered in the system, the system will return the assignment for the patient. This study will use a “permuted block” randomization scheme where random block sizes of two and four will be used. The research coordinator will need the following information in order to complete a successful randomization call:

- a. Study number and study password (will be provided by CSPCC)
- b. 3-digit site number and password (will be provided by CSPCC)
- c. The subject's ID Number & ALPHA Code
- d. The subject's signed Informed Consent Form
- e. Form 01, Screening and Randomization
- f. Laminated Randomization Cheat Sheet

a. Data Capture during visits and/or telephone contacts

The system for data capturing will be designed by visits where a group of required CRFs will be assigned to each “visit” according to the “Schedule of Assessments” table.

FORM	SCREEN	BASELINE (pre op)	INTRA OP	POST OP	DC- 30 DAY	6 WK	3 MO	6 MO	9 MO	12 Mo	...	45 MO	49 MO	AS NEEDED
00-Screening Log	X													
01 – Screening and Randomization	X													
02 – Baseline Information		X												
03 – Seattle Angina Questionnaire		X				X				X				
04 – VR-12		X				X				X				
05 – Intraoperative Data Collection			X											
06 – Post Operative Assessments				X										
07 – Discharge Assessments					X									
08 – Leg Incision Pain Questionnaire					X									
09 – Leg Incision Pain 6 Week						X								
10 – Leg Incision Assessment					X	X								
11 – Mace Event (6 Week)						X								
12 – Phone Call Follow-up							X	X	X	X	X	X	X	
13 – MACE Event Form													X	
14 - Termination														X

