Answers to questions 6-13 must all be 'NO' for the subject to be eligible for enrollment

SITE NO.			
----------	--	--	--

SUBJECT ID			
------------	--	--	--

ALPHA CODE			
------------	--	--	--

ENROLLMENT

No Yes

14. Is the subject eligible to be enrolled into the REGROUP study? *If the answer to question 14 is NO, then STOP, SIGN form - this form is now complete.*15. If the subject is **eligible but not enrolled**, mark (x) in the one box that best describes the reason:

- Subject refused to sign Informed Consent*
- Eligibility status changed (e.g., died, treatment plan changed, etc.)*
- Site surgeon concerned about resources needed for on-site follow-up (cost, time, etc)*
- No reliable method of follow-up contact with the subject (e.g., no phone, etc.)*
- Primary reason subject preferred non-enrollment*
 - Subject prefers open vein harvest*
 - Subject prefers endoscopic vein harvest*
 - Reason other than vein harvest preference*

specify: _____

- Primary reason surgeon preferred non-enrollment*
 - Surgeon prefers open vein harvest for subject*
 - Surgeon prefers endoscopic vein harvest for subject*
 - Reason other than vein harvest preference.*

specify: _____*If the subject was not enrolled in the study, STOP, SIGN form - this form is now complete.***RANDOMIZATION** - If the subject is eligible and willing to be randomized, call CSPCC at [contact]

No Yes

16. Was the subject randomized into the study? *If Q 16 is Yes then go to Q 18. If Q 16 is No then go to Q 17 and the form is complete when signed.*

--	--	--

--	--	--	--

--	--	--	--

17. If the subject has signed the consent but was not randomized, mark (x) in the one box that best describes the reason:

Eligibility status changed

explain: _____

Subject changed mind after consent signed

explain: _____

Surgeon changed mind after subject signed consent

explain: _____

Other reason (specify): _____

18. If the subject is **randomized**, complete the following information:

a. Date subject was randomized

--	--

--	--

--	--	--	--

Month Day Year

b. Time subject was randomized (Military Time)

--	--

--	--

hour : min

c. Assigned harvester ID Number

--	--

d. Assigned surgeon ID Number

--	--

e. Envelope Number

--	--

 -

--	--	--	--

f. To what treatment was subject randomized?

--

 EVH

--

 OVH

--

S.I. or Participating Surgeon Signature _____

Print Name: _____

Print name of the person completing this form if other than the site coordinator: _____

SITE NO.

--	--	--

SUBJECT ID

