VA COOPERATIVE STUDY #588

RANDOMIZED ENDO-VEIN GRAFT PROSPECTIVE – REGROUP TRIAL

Site Selection Process: Vein Harvester Qualification Policy

1. VA sites with active Cardiac Surgery Programs are contacted with introductory letter including executive summary and relevant manuscripts via email.
2. Interested sites provide high-level overview of the sites Cardiac Surgery Service eligibility criteria:
 - established EVH program >2years,
 - sufficient isolated CABG volume to enroll 2-3 subjects/month x3 years,
 - willingness to randomize to EVH vs. OVH,
 - at least one harvester experience includes > 100 EVH with conversion rate \leq 5%,
 - ability to competently provide care for OVH procedure.
3. All potential sites complete CSP #588 Form 15 for each individual harvester who is expected to perform the vein harvesting procedure as part of normal daily job duties during the course of study participation at the site. The forms are signed by the site Principle Investigator (site surgeon investigator) as verification.
4. Each completed form is submitted to and reviewed by the Study Chair's office.
5. A Subcommittee of the Executive Committee will review each site case by case to determine eligibility status and designate each site as one of the following:
 - A. Site with at least one harvester experienced in BOTH EVH and OVH confirmed by the site surgeon investigator => site confirmed as qualified for study participation and harvester assigned a code by CSPCC.
 - B. Site with at least one harvester experienced in EVH but NOT OVH confirmed by the site surgeon investigator => site confirmed as qualified for study participation only IF a designated harvester for OVH is identified, assigned a code by CSPCC, and MUST be immediately available, in addition to the EVH harvester, at time of randomization and harvesting (i.e. the site surgeon investigator).
 - I. Site with NO harvester experienced in EVH and/or incapable of providing OVH procedure=> site is INELIGIBLE for study participation at this time regardless of interest level or CABG volume.

Subcommittee Members: [name] [name], FETCS; [name], PA-C; [name], CRNP

CSP #588

RANDOMIZED ENDO-VEIN GRAFT PROSPECTIVE – REGROUP TRIAL

Version 1.2 Protocol

October 1, 2013

F-1

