3.4 Randomization and Blinding

A block randomization scheme will be used to randomize participants in two treatment groups. The block randomization technique will ensure equal distribution of participants, within each harvester, within each medical center, in both arms of the trial. A random sequence of block sizes will be used to reduce the chances of guessing future allocations. The randomization schema will be generated using SAS (SAS, Cary, NC). All participating vein harvesters must meet the minimum EVH/OVH volume criteria [at least 100 EVH cases with low conversion rates (<5%) as part of an EVH program established for more than two years] to be eligible to enroll patients in this study. Unless an urgent medical condition exists, the participant's surgery will be scheduled to occur at the earliest possible date based on expert harvester availability and other center circumstances. The randomization procedure will occur after the participating expert harvester is assigned to the participant. Participants will be randomized within the assigned participating harvesters to one of the two study harvesting technique arms (EVH or OVH). Recognizing that the participant's assignment to a participating vein harvester will have already occurred, the study randomization to either EVH or OVH will be done by a telephone call to the Perry Point Cooperative Studies Program Coordinating Center (CSPCC).

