equality (null hypothesis) of the survival function estimates across strata (OVH and EVH) will employ either the log-rank or Wilcoxon test. Multivariable survival analyses applying a Cox proportional hazards regression model will be performed to investigate the effect of SVG harvesting technique on time-to-MACE, adjusting for other potentially influential baseline characteristics, such as age, gender, harvester's experience, etc. (TABLE 25). Assumptions of the model (i.e., non-informative censoring, proportional hazards) will be checked. If assumptions appear to be violated, alternative methods will be explored (e.g., piecewise, time-varying covariates). A type I error rate of $\alpha = 0.05$ will be used throughout. Confidence intervals will be two-sided with a 95% confidence level.

The hypothesis for the primary aim of this study is:

H1: A significantly smaller proportion of CABG subjects with SVGs harvested by open technique will experience MACE post-surgery compared to CABG subjects with SVGs harvested by endoscopic technique during the active follow-up period.

The hypothesis for the primary aim of this study will be supported when an increased risk of MACE is observed among participants randomized to EVH, confirmed with a hazards ratio (HR) > 1.00 for EVH vs. OVH and a significant corresponding p -value $< \alpha$.

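### Randomisation is stratified by harvester within site, but the primary test, the Cox model and the one- and three-year MACE tests do not use site or harvester; stratifying by site is a small, nearly free gain

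*Protocol*

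**What the plan says.** **Allocation.** Protocol VI.C: "Randomization to either the EVH or OVH technique, stratified by harvester within site, will occur at the time of surgery". Protocol Appendix D (Randomization) and SAP 4.2 give the blocking: "random block sizes of two and four will be used". SAP 3.4 repeats randomisation within the assigned harvester. The SAP Table 11 shell lists 32 harvesters at the 16 centers.

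**Primary analysis.** Protocol XVII.D.2, repeated in Appendix D: "a log-rank statistic will be used to test the equality of the survival function estimates in the two groups". SAP 7.1 puts the test this way: "equality (null hypothesis) of the survival function estimates across strata (OVH and EVH) will employ either the log-rank or Wilcoxon test". The strata in that sentence are the two arms, not the randomisation strata.

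**Cox model.** Both documents name age, gender and harvester's experience and leave the list open. Appendix D adds a screening step for predictors. Site could therefore enter, but nothing commits to it, and harvester identity is not mentioned.

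**One- and three-year MACE.** Protocol XVII.D.3: "These two proportions will be compared using a chi-square test". SAP 7.2 specifies Pearson's chi-square. Neither mentions strata.

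Site and harvester identity otherwise appear only in descriptive tables.

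**The concern.** Blocking within strata removes between-stratum differences in risk from the arm comparison. A pooled test still counts those differences as noise, so its variance is slightly too large. The result is a true size a little under 5% and some lost power. Type I error is not inflated.

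Stratum differences are plausible here. The protocol's background describes endoscopic harvest as operator dependent, and harvester experience is a stated objective. What is at stake is efficiency, mainly if the true effect is smaller than planned. That possibility is real on the protocol's own evidence: section I cites an adjusted hazard ratio of 1.22 from the PREVENT-IV analysis, and section II cites a large registry analysis with no difference.

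**Working it through.** **1. The plan's own figures (Protocol XVII.B).**
- One-year MACE 9.5% vs 15.5%, two-sided 5%, 85% power, pooled-variance formula without continuity correction: 544.01, rounded up to 545 per group, as stated. Then 1,090/0.95 = 1,147.
- Time to MACE: hazard ratio (OVH:EVH) = ln 0.915 / ln 0.835 = 0.493. Freedman's formula at 97.5% power gives [(1.493/0.507) × (1.960 + 1.960)]² ≈ 133 events. With a mean event rate of 12.5%, 133/0.125/2 = 532 per group, as stated.

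Neither figure depends on stratification, and neither is disputed.

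**2. Size of the pooled test, analytically.** Let ICC be the share of outcome variance lying between strata. With balance inside strata, actual α = 2[1 − Φ(1.96/√(1 − ICC))]. At a 12.5% event rate:

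| SD of site log-odds | 5th-95th percentile site rate | ICC | actual α |
|---|---|---|---|
| 0.3 | 7.8-18.5% | 0.0099 | 4.89% |
| 0.5 | 5.4-22.9% | 0.0275 | 4.69% |
| 0.8 | 3.0-29.8% | 0.0693 | 4.22% |

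**3. Simulation A.** The design is 16 sites × 72 = 1,152 participants, with harvesters per site from SAP Table 11 (1, 2, 1, 3, 3, 2, 3, 2, 1, 2, 1, 3, 2, 2, 1, 3 = 32) and blocks of 2 and 4 within harvester. Entry is uniform over 3 years, follow-up runs 1-4 years, and hazards are constant. Stratum effects are normal on the log-hazard, placed either all at harvester level or half the variance at site and half at harvester; ranges span the two. There were 10,000 trials per cell, with all tests run on the same trials. Log-rank power (%):

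| True effect | SD | Pooled | By site | By harvester |
|---|---|---|---|---|
| HR 2.03 (= 1/0.493; about 140 events) | 0 | 98.7 | 98.7 | 98.7 |
| | 0.75 | 97.0-97.3 | 97.2-97.5 | 97.2-97.6 |
| HR 1.45 (assumed; about 250 events) | 0 | 84.5 | 84.1 | 83.6 |
| | 0.25 | 83.7 | 83.4 | 83.1 |
| | 0.5 | 81.3-81.6 | 82.0-82.4 | 82.3-82.7 |
| | 0.75 | 76.2-76.9 | 78.8-79.2 | 79.7-80.8 |
| HR 1.22 (PREVENT-IV; about 180 events) | 0 | 26.9 | 26.5 | 26.2 |
| | 0.75 | 22.3-22.7 | 24.3-24.4 | 25.0-25.2 |

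- At HR 1.69 (= ln 0.845 / ln 0.905, the one-year planning rates), site stratification changes power by 0.1 point or less up to SD 0.5 and gains 0.3-0.5 point at 0.75.
- Size of the pooled log-rank, with 243-262 events under the null: 5.0% (SD 0), 4.7-4.9% (0.25), 4.1-4.6% (0.5), 3.9% (0.75).
- One-year 9.5% vs 15.5%, Pearson vs Cochran-Mantel-Haenszel by site: 86.8 vs 86.8 (SD 0), 85.4-86.1 vs 86.0-86.4 (0.5), 83.1-83.3 vs 84.3-84.4 (0.75).

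**4. Simulation B.** Same layout, but with marginal event rates held fixed and heterogeneity at site level; 12,000 null and 4,000 alternative trials per cell.
- Size, pooled / by site: 5.3/5.3% (SD 0), 5.0/5.1% (0.3), 4.6/4.9% (0.5), 4.2/5.0% (0.8).
- Power at the planned 16.5% vs 8.5%: 98.8/98.8% (SD 0) and 98.9/99.1% (0.8).
- Power at a smaller effect, 16.5% vs 11%: 79.0/78.7% (SD 0), 79.3/80.0% (0.5), 79.2/82.1% (0.8).

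**5. Wilcoxon.** A further run of 2,000 trials per cell gave a size of about 3.5-3.8% at SD 0.75 for the pooled log-rank and Wilcoxon tests, against about 5% for the site-stratified log-rank.

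**The case against.** The strongest objection is that this is a preference and not a flaw. At the planned effects nothing material changes. Any gain needs both a smaller effect than planned and heterogeneity that the documents do not support with a figure. An SD of 0.5 on the log-hazard is already about a 5-fold hazard range between the 5th and 95th percentile strata (exp(2 × 1.645 × 0.5) = 5.2); 0.75 is about 12-fold. At SD 0 to 0.25 stratifying loses a little power. All of that stands, and it is why the point is optional.

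Four narrower points:

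- **The Cox model was not simulated.** It may absorb part of the harvester variation through the experience covariate. The statement about Cox is therefore only that nothing commits it to site or harvester; how conservative it would be is not quantified.
- **Sparse strata are a weak reason to prefer site.** About 141 events give 141/16 = 8.8 per site and 141/32 = 4.4 per harvester. That count corresponds to reaching the 83.5%/91.5% rates at about 2.5 years. The one-year planning rates instead give about 319 events over 1-4 years of follow-up, or about 20 and 10.
- **Harvester strata can do better.** They beat site strata in Simulation A at HR 1.45 once SD reaches 0.5. When all heterogeneity is at site level (Simulation B, SD 0.8), site is slightly ahead, 82.1% vs 81.7%.
- **A site-stratified hazard ratio is conditional on site** and need not match the unadjusted Kaplan-Meier curves. This is true and should be said when reporting.

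The main reason for choosing site survives. Protocol XIV and Appendix F allow a different person to do the open harvest. Where the EVH harvester is not experienced in OVH, Appendix F says of the designated open harvester: "MUST be immediately available, in addition to the EVH harvester, at time of randomization and harvesting". A harvester stratum is then not one operator in both arms.

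**Conclusion.** The concern holds as a minor efficiency point. The planned tests are valid, with size at or below 5%, and 545 and 532 per group both reproduce. Ignoring the randomisation strata costs essentially nothing at the planning effects. At HR 1.45, site stratification gains roughly 0.4-1.1 points at SD 0.5 and 2-3 points at SD 0.75. If strata are not prognostic, it costs up to 0.4 point with site strata and up to about 1 point with harvester strata. These sizes rest on an assumed between-stratum SD, constant hazards, uniform entry and equal splits within site. The unsettled choice between log-rank and Wilcoxon in SAP 7.1 is a separate and more consequential matter, and it adds no weight here.

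**What to change.** - In Protocol XVII.D.2, Appendix D and SAP 7.1, name one primary test: a two-sided log-rank test of EVH vs OVH stratified by medical center.
- Report the treatment hazard ratio and 95% CI from a Cox model stratified by medical center, and note that it is conditional on center.
- For one- and three-year MACE (Protocol XVII.D.3, SAP 7.2), use a Cochran-Mantel-Haenszel test stratified by medical center.
- Keep as sensitivity analyses the log-rank test stratified by harvester within site, using the harvester assigned at randomisation, and the unstratified log-rank and chi-square tests.

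No new data are needed. Form 01 already carries the site number and, at question 18c, the "Assigned harvester ID Number". The work is SAP wording and a stratification term in the code. The power cost if sites do not differ is up to 0.4 point for the log-rank test and 0.1 point or less for the one-year test.
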